5.2 Study Duration

Study participation will last approximately 4-5 weeks, consisting of a screening/baseline visit, treatment/lumbar puncture visit, a follow-up/final assessment visit.

5.3 Study Drug Administration

5.3.1 Drug Administration with SipNose

REDACTED

5.3.2 Device Dose Loading and Administration

REDACTED

6 Study Population

6.1 Eligibility Criteria

6.1.1 Inclusion Criteria

A subject will be included for consideration in this study only if all the following criteria are met:

1. Subject is between ≥ 18 and ≤ 35 years of age
2. Subject's BMI is between ≥ 18.5 and ≤ 24.9 , or can safely undergo a lumbar puncture at the discretion of the radiologist
3. Subject must be proficient in speaking English to comply with instructions and measures for the study
4. Subject can provide written informed consent
5. Female subjects must have either: (1) a negative pregnancy test at the screening visit and treatment visit OR (2) be at least 2 years post-menopausal / surgically sterile.

6.1.2 Exclusion Criteria

A subject will *not* be included for consideration in this study if any of the following criteria are met:

1. Subject has medical history and/or clinically determined disorders: chronic sinusitis, previous nasal and/or oto-pharyngeal surgery and severe deviated septum and/or other anomalies.

2. Subject has history of any of the following: active and significant central nervous system, psychiatric illness, pulmonary, or cardiovascular disorders or any other clinically relevant abnormality that inclusion would pose a safety risk to the subject as determined by investigator
3. Subject has participated in a clinical trial investigation within 3 months of this study.
4. Subject has an insulin allergy
5. Subject has Insulin-dependent diabetes
6. Subject is pregnant or breast feeding
7. Contraindication to spinal tap or other safety factors that preclude lumbar puncture in the investigator's opinion

7 Study Assessments and Procedures

A summary of study events and procedures is outlined in the Study Visit Table (Table 3).

7.1 Demographic and Baseline Assessments

7.1.1 Screening Visit 1

The following procedures will be performed at this visit: This may also be divided into two parts, with virtual and in-person visits. Virtual activities (e.g., consent, review of medical history/medications) can be completed on a separate day(s) from other study procedures, provided that consent occurs within 3 months of the lumbar puncture and all other screening activities are completed within the specified window (21-7 days prior to lumbar puncture visit/Visit 2). All activities will take approximately 2 hours to complete. No study procedures, virtual or otherwise, will be completed until a fully executed consent form has been obtained. Participants will be given the option to have a dose of sterile saline administered by research staff using the device if they want to experience the sensation of the device before the lumbar puncture visit.

- Obtain written informed consent Review Inclusion/Exclusion Criteria
- Review medical history, as it pertains to inclusion/exclusion criteria
- Pregnancy test for women of childbearing potential
- Review guidance on the use of effective birth control from the time of study enrollment until 30 days **after** the final visit.
- Obtain subject's demographic information (date of birth, gender, race, and ethnicity).
- Collect vital signs, height and weight
- Obtain details of medications taken over the course of the last 30 days
- Physical/neuro examination including examination of the nares and nasal passages
- Blood draw for laboratory investigations
- C-SSRS
- 12-Lead Standard ECG
- Saline test dose (optional)
- Pre-procedure instructions
- Provide Information sheet provided relating to pre-lumbar puncture hydration
- Visit #2 scheduled after 2 weeks \pm 7 days

7.1.2 Lumbar Puncture Visit 2: In-Person Visit (2 week \pm 7 days after Visit 1)

The subject will be check in at the Regions Hospital outpatient care unit (OPCU). The visit will be at the General Radiology Department (where the lumbar puncture will be performed and study data collected) and will return to the OPCU for post-operative monitoring.

The following procedures will be performed at this visit:

- Review Inclusion/Exclusion Criteria
- Collect concomitant medication information and record AEs/SAEs
- Collect vital signs and weight
- Pregnancy test for women of childbearing potential
- Review guidance on the use of effective birth control until 30 days study **after** the final visit.
- Glucose finger stick test (once before study drug administration and twice after)
- Clinician will discuss procedure with the subject
- Lumbar puncture and collection of CSF for insulin
 - CSF samples will be obtained at predefined times (0-40 min). CSF samples will be collected FIRST at all time points.
- Blood draw and collection of serum for insulin
 - Serum samples will be obtained at predefined times (0-40 Minutes). CSF Samples will be collected SECOND at all time points.
- Study Drug administration
- Nasal Irritation Scale
- Patient will lay on back for a total of 2 hours post-lumbar puncture
- Visit #3 scheduled within a week \pm 5 days

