4.3 Safety

- Incidence and severity of serious adverse events (SAEs) and adverse events (AEs)
- Frequency of change in clinically-significant vital signs
- fingerstick glucose level <70mg/dl

5 Study Design

This Phase 1 is a single center, open-label, randomized pharmacokinetic study designed to describe the central nervous system delivery of intranasal insulin to CSF using anIN delivery device.

Table 1: Study Design

INI Insulin Dose	Collection Times
40 IU (n=6) 2 x 200 μ L (0.2ml)	0, 10, 20, 30, 40 min
80 IU (n=6) 2 x 200 μ L (0.2ml) Wait 2 min 2 x 200 μ L (0.2ml)	0, 10, 20, 30, 40 min

After written informed consent has been obtained, subjects will be screened to assess study eligibility based on study inclusion/exclusion criteria. Subjects who are eligible at the end of the screening visit will be randomized and assessed for outcome measures, including lumbar puncture and CSF/blood draw following a single dose of INI administered by the trained research staff. Randomization will be stratified by gender to ensure a balanced distribution of male and female participants within each group. A Block randomization scheme will be employed to ensure that the final group sizes are equivalent.

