7.1.2.1 Fluoroscopy-Guided Lumbar Puncture Procedure

CSF samples will be collected according to standard operating procedures for fluoroscopy-guided lumbar puncture as observed by the General Radiology department at Regions Hospital. The procedure will be performed by a trained clinician (i.e., an interventional radiologist or an experienced member of their team), who will obtain verbal consent (in addition to the research informed consent obtained/documentated at Visit 1). CSF will be collected serially using gravity drainage. Sterile extension tubing connected to the LP needle will dispense CSF into sterile collection tubes for pharmacokinetic analysis. Samples will be collected at 5 times: once prior to the administration of a single dose of intranasal insulin and at once each at 10, 20, 30, and 40 minutes post-drug administration. Approximately 1-2ccs of CSF will be collect at all 5 time points for a total of 10ccs of CSF. The tubing connected to the needle will be flushed out between sample collections to avoid contamination between specimen timepoints. The subject will lie in prone position throughout the procedure with appropriate measures taken to minimize discomfort (e.g., provision of warm blankets, use of positioning sponges, etc.).

Subjects will lie on their back 2 hours after the procedure for standard-of-care monitoring with nursing staff, and periodic collection of vital signs. Participants will receive instructions from the clinical team on techniques for preventing and treating post-LP headache (e.g., drinking water and caffeinated beverages, using over-the-counter pain medications). They will also receive guidance on when to seek additional help for their headache and/or any other emergent symptoms requiring immediate medical attention such as fever, persistent headache, and weakness/numbness of the lower extremities. Subjects will receive a safety assessment phone call from study staff 1 day after the procedure.

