7.3.11 Pharmacokinetic Sampling

The study team will attempt to collect the CSF and serum samples as close in time as possible for each PK time point. Given differences in how serum/CSF are extracted for this study, there may be a slight difference between collection start and stop times. To ensure consistency across participants, the study team will initiate collection of the CSF samples first, followed by the serum samples, at each of the 5 PK time points.

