12.2 Statistical Analysis of Primary and Secondary Endpoints

Primary Endpoints: We will utilize immunoassay to analyze the CSF samples to determine the levels of Insulin concentration at the specified times. We will graph these values across time for each subject using line graphs. We will also graph the sample average Insulin concentration across time, and at different doses with error bars and report concentrations as mean \pm SE. Finally, the concentrations will be analyzed using common pharmacokinetic measures including the peak concentration (Cmax), time to peak concentration (Tmax), and area under the curve (AUC). This type of analysis is very similar to that done in Dhuria's 2009 publication in the *Journal of Pharmaceutical Sciences*, on which [name] and [name] were co-authors. Similar analysis will be conducted for secondary endpoints.

AEs and SAEs will be categorized and summarized by study group. We will descriptively note if any group was more likely to have experienced a particular AE/SAE or generally experienced more AEs/SAEs throughout the course of the study.

13 Study Conduct Considerations

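### Correct the Visit 2 sampling-order line, then record actual CSF and serum collection times and use them for individual profiles, Tmax and AUC

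*Combined protocol and SAP*

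**What the plan says.** **Order of collection.** In the Section 7.1.2 list for Visit 2, the CSF bullet says "CSF samples will be collected FIRST at all time points". The serum bullet that follows says "CSF Samples will be collected SECOND at all time points". Section 7.3.11 says "the study team will initiate collection of the CSF samples first, followed by the serum samples, at each of the 5 PK time points".

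**How CSF is taken.** Section 7.1.2.1: "CSF will be collected serially using gravity drainage". Each of the five samples is about 1-2 cc, taken through extension tubing that is flushed between samples. One sample is pre-dose; the others are at 10, 20, 30 and 40 minutes after administration.

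**Timing.** Section 7.3.11: "Given differences in how serum/CSF are extracted for this study, there may be a slight difference between collection start and stop times". Section 12.2: "We will utilize immunoassay to analyze the CSF samples to determine the levels of Insulin concentration at the specified times". It then plans individual and mean line graphs, Cmax, Tmax and AUC, and a similar analysis for serum.

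**Dosing.** In Section 5, Table 1, the 40 IU arm receives two 0.2 mL sprays. The 80 IU arm receives two, then "Wait 2 min 2 x 200" µL. Sections 5.3.1 and 5.3.2, on drug administration, are redacted in the public copy.

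**Dose and puncture.** Section 7.3.6 has the dose given before the lumbar puncture. Section 7.1.2.1 requires a CSF sample before the dose, and Section 8.4 has staff assist with pre-dose sampling once needle placement under fluoroscopy is over.

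**The concern.** CSF insulin at set times is the primary endpoint, with six participants per arm and a 10-minute grid. A drained sample is an average over its collection period, not a reading at one instant. If collection starts at the nominal time and lasts several minutes, the value belongs to a later moment, and the shift varies with each participant's drip rate. Serum follows CSF, so it may run later still. Other tasks fall close to the same slots: finger-stick glucose at 15 and 45 minutes, and nasal irritation scores at 20 and 40 minutes.

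The 10-minute sample is the most exposed, because a shift of a few minutes is a large share of the time since dosing. It also matters most to the rationale, since Section 1.1.1 cites CSF insulin detected as early as 10 minutes. The 2-minute wait occurs in the 80 IU arm only, so it falls unequally on the two doses. Times that are not written down on the day cannot be recovered.

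**Working it through.** The plan gives no figure to reproduce here. The check is a reading of the text followed by a sensitivity calculation.

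**1. Order.** Two statements put CSF first (the CSF bullet in 7.1.2, and 7.3.11). One puts it second, and that one sits under the serum bullet. Replacing CSF by serum in that line makes all three agree.

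**2. Collection time.** From the protocol: 1-2 mL per sample. The flow rate is not stated. Assuming 0.2 to 2 mL/min, the time is volume/flow: from 1/2 = 0.5 min to 2/0.2 = 10 min. I use 1-5 min as the working range and 10 min as an extreme.

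**3. Effect of treating a drained sample as a point sample.** Assumed curve: C(t) = ka/(ka - ke) × [exp(-ke·t) - exp(-ka·t)], which peaks at ln(ka/ke)/(ka - ke). With (ka, ke) per minute of (0.2, 0.05), (0.08, 0.03) and (0.04, 0.015), the peaks fall at 9.2, 19.6 and 39.2 min. The collected value is the mean of C over [t, t+D], with collection starting at the nominal time. The pre-dose value is set to 0. AUC0-40 by trapezoid is 10 × (C10 + C20 + C30) + 5 × C40.

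Example, late peak, D = 5: C(10) = 0.305; the mean over 10-15 min is 0.355; 0.355/0.305 = 1.16.

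| D (min) | Change in 10-min value: early / mid / late peak | Change in AUC0-40: early / mid / late peak |
|---|---|---|
| 1 | -0.5% / +2.2% / +3.6% | -1.5% / +0.2% / +1.1% |
| 2 | -1.2% / +4.2% / +7.0% | -3.0% / +0.3% / +2.2% |
| 5 | -4.3% / +9.0% / +16.4% | -8.0% / +0.2% / +5.1% |
| 10 | -11% / +14% / +30% | -16% / -1% / +9% |

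For D of 1-5 min the sample with the highest value is unchanged in all three profiles. At D = 10 it moves one step (40 to 30 min) in the late-peak profile only. Other peaked curves shift the 1-5 min limits by about a percentage point, to -5% and +17% at 10 min and to -7% and +5% for AUC.

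**4. Upper bound.** Suppose instead that the level rises linearly after a lag of 0 or 5 min. With D = 5 the 10-min value is 12.5/10 = 1.25 or 7.5/5 = 1.50 times the point value, and AUC is 1.11 or 1.14 times.

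**5. What midpoint times do.** For D of 1-5 min, each collected value at 10 min lies within 0.6% of the curve at the collection midpoint, so the concentration is attached to the right time. AUC does not improve everywhere. With D = 5, midpoint times, and the area cut at 40 min by interpolation, AUC differs from the point-sample trapezoid by -5.8%, -2.0% and -0.8%. At nominal times it differs by -8.0%, +0.2% and +5.1%. That is better in two profiles and slightly worse in one.

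**6. Split dose.** Take a true 80/40 ratio of 2 and the linear rise. Timed from the first spray, the 10-min ratio is (10 + 8)/10 = 1.8 with no lag, or (5 + 3)/5 = 1.6 with a 5-min lag. Timed from the last spray it is (10 + 12)/10 = 2.2, or (5 + 7)/5 = 2.4. The AUC ratio is 1.89-1.91 or 2.09-2.11. With the peaked curves the 10-min ratio is 1.84-1.99 or 1.97-2.14, and the AUC ratio 1.95-2.05 or 1.94-2.04.

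**The case against.** The strongest reply is that this is editorial. Section 7.3.11 settles the order, so a reader who infers from 7.1.2 that CSF timing is compromised goes too far: the line is a slip and bears mainly on how CSF and serum values pair. That stands.

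A reader might also infer that the 80 IU dose has no time zero. The documents do not support this. Sections 5.3.1 and 5.3.2 are redacted, and the spray sequence and clock start could be there. Only the readable text is silent.

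A reader might infer that Section 12.2 assigns every value to its nominal time. It does not say so; it does not state which time enters Tmax and AUC. Section 13.7 leaves data-collection forms to be developed, and these may already capture clock times.

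The analysis is descriptive, with no dose-ratio estimate or test. A collection delay common to both arms largely cancels between them. Assuming a between-subject CV of 20-60%, the standard error of a ratio with six per arm is about CV × √(2/6), or 12-35%. The split-dose effect on AUC is small beside that.

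These replies limit the size of the point. They do not remove the contradictory line or the missing rule for sample times. A systematic shift in the early samples is also not averaged out by adding participants.

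**Conclusion.** The point holds in limited form. The serum bullet in 7.1.2 is wrong against 7.3.11. No readable section requires actual collection times or says how a drained sample is timed, so early concentrations, and AUC to a lesser degree, could be mis-timed. It is not established that they are, because the documents give neither flow rate nor collection duration.

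With assumed collections of 1-5 minutes starting at the nominal time, and assumed one-compartment curves, the 10-minute value moves by roughly -4% to +16% and AUC0-40 by -8% to +5%. Even the direction depends on the curve; the linear rise gives a larger upper bound. The stronger inference that Tmax is wrong has no support: the peak sample did not move for 1-5 minute collections, and the grid is already coarse.

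The 2-minute wait affects the 10-minute dose comparison whichever spray starts the clock. Fixing time zero labels that effect and does not remove it.

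Separately, Section 7.3.6 conflicts with Sections 7.1.2.1 and 8.4 on whether the dose precedes the lumbar puncture. These sections must be reconciled.

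**What to change.** 1. In 7.1.2, change the order statement in the serum bullet so that it refers to serum, matching 7.3.11.
2. Add worksheet fields for the start and stop clock time of each CSF collection, the time of each serum draw, and the first and last spray times.
3. In 12.2, state that individual profiles, Tmax and AUC use actual times: the collection midpoint for CSF and the draw time for serum. Keep nominal times for the mean plots only. Say how AUC is cut at 40 minutes when the last midpoint falls later.
4. Confirm that Section 5.3 sets the same time zero for both arms. Note in 12.2 that the 10-minute comparison between doses is affected by the split administration.
5. Reconcile 7.3.6 with 7.1.2.1 and 8.4 on the sequence of dose, puncture and pre-dose sample.

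Items 1-4 cost one corrected line, a few time fields, a few sentences in 12.2 and slightly more analysis work. They change neither dosing nor the sampling schedule.

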7.1.2.1 Fluoroscopy-Guided Lumbar Puncture Procedure

CSF samples will be collected according to standard operating procedures for fluoroscopy-guided lumbar puncture as observed by the General Radiology department at Regions Hospital. The procedure will be performed by a trained clinician (i.e., an interventional radiologist or an experienced member of their team), who will obtain verbal consent (in addition to the research informed consent obtained/documentated at Visit 1). CSF will be collected serially using gravity drainage. Sterile extension tubing connected to the LP needle will dispense CSF into sterile collection tubes for pharmacokinetic analysis. Samples will be collected at 5 times: once prior to the administration of a single dose of intranasal insulin and at once each at 10, 20, 30, and 40 minutes post-drug administration. Approximately 1-2ccs of CSF will be collect at all 5 time points for a total of 10ccs of CSF. The tubing connected to the needle will be flushed out between sample collections to avoid contamination between specimen timepoints. The subject will lie in prone position throughout the procedure with appropriate measures taken to minimize discomfort (e.g., provision of warm blankets, use of positioning sponges, etc.).

Subjects will lie on their back 2 hours after the procedure for standard-of-care monitoring with nursing staff, and periodic collection of vital signs. Participants will receive instructions from the clinical team on techniques for preventing and treating post-LP headache (e.g., drinking water and caffeinated beverages, using over-the-counter pain medications). They will also receive guidance on when to seek additional help for their headache and/or any other emergent symptoms requiring immediate medical attention such as fever, persistent headache, and weakness/numbness of the lower extremities. Subjects will receive a safety assessment phone call from study staff 1 day after the procedure.

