7.3.2 Neurological Examination

Neurological examination will be performed at visits 1, 3 or if the subject withdraws early. Any abnormalities noted at Visit 1, will be documented as part of the subject's medical history.

7.3.3 Vital Signs:

Vital signs will be recorded at all three study visits. Diastolic blood pressure will be measured at the disappearance of Korotkoff sounds. Vitals sign will be monitored by clinical staff during screening and lumbar puncture visits of the study.

Serum Glucose will be examined at visit 1 (screening) and visit 3 (safety follow-up). Fingerstick glucose tests will be performed at visit 2 (LP procedure). A blood glucose < 70 mg/dL will be considered clinically significant. The likelihood of peripheral hypoglycemia is low based on numerous clinical trials performed showing no effects of INI on peripheral glucose.

7.3.4 Weight:

Body weight will be measured at all three study visits.

7.3.5 Laboratory Samples:

All the laboratory samples will be drawn independent of fasting or non-fasting status.

When a patient withdraws from the study, samples collected prior to the date of withdrawal may still be analyzed, unless the patient specifically requests that the samples be destroyed or local laws require destruction of the samples. However, if samples have been tested prior to withdrawal, results from those tests will remain as part of the overall research data. Samples will be collected and processed according to the standard procedures. Key planned labs include:

- Basic Metabolic Panel
- Complete Blood Count
- Blood Coagulation Tests

7.3.6 Point-of-Care Glucose Testing:

At Visit 2, the participant will receive a single dose of intranasal insulin administered prior to their lumbar puncture. Point-of-care fingerstick glucose testing will be performed once before the administration of the study drug (baseline glucose reading) and twice after the administration of the drug according to the following schedule:

- (1) 15 minutes after study drug dosing (between the 2nd and 3rd CSF/serum samples are collected)
- (2) 45 minutes study drug dosing (after the final CSF/serum samples are collected)

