7.3.11.1 CSF Sampling

It is our intention to collect samples at pre-defined times following a single dose administration. CSF will be collected at 0, 10, 20, 30 and 40 minutes for all study participants. CSF samples will be assessed for insulin using a one-step sandwich immunoassay with a limit of detection of 0.1 µIU/ml or 0.7 pmol/L

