8.4 Occupational Safety

No known significant safety risks exist to site personnel in direct or indirect contact with the study drug. As the lumbar puncture will employ fluoroscopy, clinical (non-research) staff will be exposed to radiation. The fluoroscopy technicians and radiologist will follow standard clinical protocols for radiation safety (e.g. wearing lead Personal Protective Garments). The amount/duration of radiation exposure for this research LP is not greater than what would be experienced during a routine LP. As fluoroscopy is only needed to assist with needle placement, study staff will not need to be present for this part of the procedure and can step out of the procedure room while the fluoroscopy machine is in use. Research staff can then reenter the room to assist with pre-dose sample collection/fingerstick glucose testing after the machine has been deactivated.

9 Concomitant Medications and Non-Drug Therapies

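### The protocol guards CSF tubes against carry-over between time points but states no check for blood, so plasma insulin in a tube would be analysed as CSF insulin

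*Combined protocol and SAP*

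**What the plan says.** Section 7.1.2.1 describes gravity drainage through extension tubing into five tubes: "Approximately 1-2ccs of CSF will be collect at all 5 time points for a total of 10ccs of CSF". The one specimen safeguard is "The tubing connected to the needle will be flushed out between sample collections to avoid contamination between specimen timepoints". Collection is otherwise to be done "according to standard operating procedures for fluoroscopy-guided lumbar puncture"; that departmental procedure is not part of the document.

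Section 7.3.11.1 states: "CSF samples will be assessed for insulin using a one-step sandwich immunoassay with a limit of detection of 0.1" µIU/mL. Section 7.3.11.2 uses the same assay, with the same limit, for serum.

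Section 12.2 begins: "We will utilize immunoassay to analyze the CSF samples to determine the levels of Insulin concentration at the specified times". It then plots each subject's curve and the average by dose, reports means with standard errors, and derives Cmax, Tmax and AUC. It gives no rule for a compromised specimen and no correction for the pre-dose value. The replacement rule in section 10.2 covers withdrawals before the puncture and insufficient sample, not a contaminated one.

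On sequence, section 7.1.2.1 has the first sample taken "once prior to the administration of a single dose of intranasal insulin". Section 8.4 places it after the fluoroscopy used for needle placement: "Research staff can then reenter the room to assist with pre-dose sample collection/fingerstick glucose testing after the machine has been deactivated". Section 7.3.6 says instead that "the participant will receive a single dose of intranasal insulin administered prior to their lumbar puncture".

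**The concern.** Serum contains insulin too, and the assay reads it in both fluids. The study drug is itself human insulin, and no method is described to separate dosed from endogenous insulin or CSF insulin from plasma insulin. If puncture blood enters a tube, its plasma insulin is reported as CSF insulin.

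The design offers little to offset this. The Protocol Summary lists no control, so there is no undosed group in which the artefact would show. Each dose has six subjects. Section 7.3.5 leaves fasting status uncontrolled for laboratory samples; if that extends to Visit 2, serum insulin may be at fed levels, and less blood is then needed to matter.

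A bloody later tube could produce a false peak that looks like nose-to-CSF delivery. A bloody 0-minute tube could put Tmax at 0 and slightly raise the raw AUC. If tube appearance is not recorded at collection, that information may not be recoverable.

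**Working it through.** The plan gives no figure for blood contamination, so there is none to reproduce.

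**Inputs from the document:** detection limit 0.1 µIU/mL (7.3.11.1); tube volume 1–2 mL (7.1.2.1); samples at 0, 10, 20, 30 and 40 minutes (7.3.11.1); six subjects per dose (section 5).

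**Assumptions, not in the document:** plasma is 55% of blood (haematocrit 0.45); serum insulin S is between 5 and 100 µIU/mL.

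**Step 1. Rise in one tube.** With blood fraction f, the rise is about f × 0.55 × S, ignoring the slight dilution of the CSF itself. The fraction that adds one detection limit is f* = 0.1 / (0.55 × S).

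| S (µIU/mL) | f* | Blood in a 1 mL tube at f* | Rise at 1% blood (µIU/mL) | Rise at 0.1% blood (µIU/mL) | Shift in six-subject mean at 1% blood (µIU/mL) |
|---|---|---|---|---|---|
| 5 | 3.6% | 36 µL | 0.028 | 0.003 | 0.005 |
| 10 | 1.8% | 18 µL | 0.055 | 0.006 | 0.009 |
| 25 | 0.73% | 7 µL | 0.138 | 0.014 | 0.023 |
| 50 | 0.36% | 4 µL | 0.275 | 0.028 | 0.046 |
| 100 | 0.18% | 2 µL | 0.55 | 0.055 | 0.092 |

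Blood volumes double for a 2 mL tube. A haematocrit of 0.40 to 0.50 changes f* by about 10%: 3.3% to 4.0% at S = 5, and 0.17% to 0.20% at S = 100.

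**Step 2. Group mean.** The shift at one time point is the rise divided by 6. A rise of one detection limit gives 0.1 / 6 = 0.017 µIU/mL. At 1% blood the largest shift in the table is 0.55 / 6 = 0.092, still below one limit. Heavier contamination could exceed it: 2% blood at S = 100 adds 1.1, and 1.1 / 6 = 0.18.

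**Step 3. Individual AUC 0–40.** With 10-minute spacing, the trapezoidal rule gives the 0- and 40-minute tubes a weight of 5 minutes and the others 10. A rise of 0.1 in the 0-minute tube therefore adds 5 × 0.1 = 0.5 µIU·min/mL to the raw AUC; in the 10-, 20- or 30-minute tube it adds 10 × 0.1 = 1.0. At 1% blood and S = 50 (rise 0.275) these become 1.4 and 2.75.

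**Step 4. Cmax and Tmax.** Each rests on a single tube. If the affected tube becomes the highest of the five, both are determined by blood.

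**The case against.** The strongest reply is that silence in the protocol is not absence of control. Collection follows a Radiology procedure, section 7.3.5 refers to standard sample processing, and neither is available to read. Fluoroscopic guidance, an experienced operator, the coagulation tests and the exclusion for puncture contraindications may all make a bloody tap less likely. This stands in part: one can say only that the protocol states no check, not that no tube is inspected. But measures that lower the rate do not detect a contaminated specimen, and a clinical procedure would not set the study's analysis rule.

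Several stronger readings are tempting and are not supported:

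- **That contamination is close to certain among 12 subjects.** An assumed traumatic-tap rate of 5% to 20% gives 1 − 0.95^12 = 46% to 1 − 0.80^12 = 93% for at least one. The document gives no rate, and this is not the chance of a tube bloody enough to matter; trace blood adds less than one detection limit.
- **That one subject can overturn the primary result.** At 1% blood a six-subject mean moves by less than one detection limit over the serum range assumed. No expected CSF level is given against which to judge more.
- **That the 0-minute tube is the likeliest to be affected, hiding a post-dose rise.** The first part is inferred from the sequence in 7.1.2.1 and 8.4, which 7.3.6 contradicts. The second needs a baseline subtraction that section 12.2 does not plan.
- **That the error could never be noticed.** Individual curves and paired serum values might raise suspicion of an isolated spike, though they could not prove blood.

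**Conclusion.** The point holds as a gap in specimen quality control and in the analysis plan. Carry-over is addressed; blood in the CSF is not, and section 12.2 would take an affected value as CSF insulin.

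The size is conditional. Under the stated assumptions, one detection limit corresponds to roughly 0.2% to 4% blood in a tube. The exposure is chiefly in individual curves, Cmax and Tmax, with a smaller effect on AUC and on group means. How often a material event would occur cannot be derived from the document. This is therefore a worthwhile, inexpensive improvement to the sole primary endpoint, not evidence that the endpoint is invalid. It does not depend on which tube is affected.

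**What to change.** **Sections 7.1.2.1 and 7.3.11.1:** record a visual blood grade for every CSF tube at collection. Where volume remains once the insulin assay's need is met, add a red-cell count; the assay volume is not stated, so this may not be possible for every 1–2 mL tube.

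**Section 12.2:** keep all tubes in the primary summary. Add a pre-specified sensitivity summary of concentrations, Cmax, Tmax and AUC without flagged tubes. Fix the flagging rule before assay, for example the blood fraction at which the paired serum value would add one detection limit, f* = 0.1 / (0.55 × S). State which visual grade flags a tube that has no count. Removing flagged values from the primary summary is not recommended: with six per dose it could leave a subject without a usable Cmax or AUC.

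**Sections 7.1.2.1, 8.4 and 7.3.6:** reconcile the order of dosing and lumbar puncture.

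The cost is minor recording and laboratory work on up to 60 tubes (12 subjects × 5), and fewer time points in the sensitivity summary. There is no added procedure for participants and no change to the sample size.
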